7.2.11 Safety Assessments

There are 5 sets of safety variables identified in the protocol. A description of each variable, and the timing of the recording of the information is presented below.

- 1: Treatment Emergent Adverse Events (TEAEs)

Three categories of AEs will be presented: Pre-Treatment, Treatment Emergent, and Post-Study. An AE will be classified as:

- pre-treatment AE: if AE starts before the first randomized study medication intake (AE onset date < date of first randomized study medication intake).
- Treatment emergent AEs (TEAEs): all adverse events starting on or after the first study drug intake, up to study completion/discontinuation. TEAEs are defined as AEs with date of first randomized study drug intake \leq AE onset date \leq date of study completion/discontinuation.
- post-study AE: if AE starts after the date of completion/discontinuation (AE onset date > date of completion/discontinuation).

Additional variables to define an adverse event include the following:

- Serious AE (SAE) is defined as any AE that has the question “Is the AE serious?” marked as “Yes” on the eCRF.
- ADR is defined as any AE that has the question “Is the AE Related to Study Drug?” marked as “Yes” on the eCRF.
- Serious ADR is defined as any ADR that are also SAE
- *Severe AE*, defined as any AE that has intensity marked as “Severe” on the eCRF.
- *AE leading to study drug discontinuation*, defined as a TEAE where the action taken on the eCRF is marked as “Drug withdrawn”.
- *AE leading to death*, defined as a TEAE where the outcome is marked as “Fatal” on the eCRF.
- *Relative day of AE onset*, defined as the AE onset date – Date of first study drug intake + 1 if the AE onset date is greater or equal to date of first study drug intake. For pre-treatment AEs, the relative day is defined as the AE onset date – Date of first study drug intake. Relative day will not be calculated in case of partial/missing date of AE onset.
- *Duration of AE*, defined as the AE end date – AE onset date + 1 when the AE is resolved. If the AE is not resolved, the duration is defined as study completion date – AE onset date + 1 and the duration will be reported as “>x” in the listing. AE duration will not be calculated in the case of a partial/missing date of AE onset.

In case of missing or incomplete AE date not directly allowing allocation to any of the categories of AEs, a worst-case allocation will be done according to the available parts of the start and the stop date. The AE will be allocated to the first category allowed by the available data, according to the following order:

1. treatment emergent;
2. post-study;
3. pre-treatment.

- 2: Vital signs (systolic and diastolic blood pressure)

Vital signs (systolic and diastolic blood pressure) will be measured pre-dose from Visit 1 to Visit 4. Blood pressure measurements are continuous variables and recorded in mmHg. Change from baseline will be calculated using the pre-dose assessment on Day 1 as the baseline value.

- 3: 12-lead ECG parameters (HR, QTcF, QRS, PR)

The following parameters from 12-lead ECG will be measured at Visits 1, 2 and 4 and at the Early Termination visit:

- Heart rate (HR) (bpm);
- PR interval (msec)
- QRS interval (msec)
- QTcF interval (msec).

QTc value will be calculated using the Fridericia formula (Fridericia-corrected $QTc = \frac{QT}{\sqrt[3]{RR}}$) It will be calculated automatically by the ECG recorder.

The changes from baseline will be based on the pre-dose assessment on Day 1.

- 4: Standard blood chemistry and hematology

Blood samples will be collected for hematology and serum chemistry at Screening and Week 8. Blood samples will also be collected at Early Termination in the morning.

The following evaluations will be performed using a central laboratory:

- *Hematology test: red blood cells count (RBC), white blood cells count (WBC) and differential, total hemoglobin (Hb), hematocrit (Hct), platelets count (PLT).*
- *Serum chemistry test: blood urea nitrogen (BUN), cholesterol, triglycerides, creatinine, uric acid, aspartate aminotransferase (AST), alanine aminotransferase (ALT), Gamma-glutamyl transferase (γ -GT), total bilirubin, alkaline phosphatases, albumin, total proteins, and electrolytes (sodium, potassium, calcium, and chloride).*
- *Fasting blood glucose*
- *Serum pregnancy test (serum β -hCG) in women of child-bearing potential; results will be presented as positive or negative. Urine β -hCG from visits 1, 2, and 3 will also be presented as positive or negative.*

Complete Blood Count (abbreviation followed by the full name and units)

| | |
|--------|------------------------------|
| HCT: | Hematocrit (L/L) |
| HGB: | Hemoglobin (g/L) |
| PLATE: | Platelets ($10^9/L$) |
| RBC: | Erythrocytes ($10^{12}/L$) |
| WBC: | Leucocytes ($10^9/L$) |

Differential (abbreviation followed by the full name and units)

| | |
|--------|---------------------------------|
| BASO: | Basophil ($10^9/L$) and (%) |
| EOSIN: | Eosinophil ($10^9/L$) and (%) |
| LYMPH: | Lymphocyte ($10^9/L$) and (%) |
| MONO: | Monocyte ($10^9/L$) and (%) |
| NEUT: | Neutrophil ($10^9/L$) and (%) |

Blood Chemistry (abbreviation followed by the full name and units)

| | |
|---------|----------------------------------------|
| ALB: | Albumin (g/L) |
| ALKPH: | Alkaline Phosphatase (U/L) |
| ALT: | ALT (U/L) |
| AST: | AST (U/L) |
| BUN: | Blood Urea Nitrogen (mmol/L) |
| BILDIR: | Direct Bilirubin ($\mu\text{mol}/L$) |
| CA: | Calcium (mmol/L) |
| CHOL: | Cholesterol (mmol/L) |
| CL: | Chloride (mmol/L) |

CREAT: Creatinine ($\mu\text{mol/L}$)
GGT: Gamma-GT (U/L)
GLUC: Fasting Serum Glucose (mmol/L)
K: Potassium (mmol/L)
NA: Sodium (mmol/L)
PROT: Total Protein (g/L)
TRIG: Triglycerides (mmol/L)
URATE: Urate ($\mu\text{mol/L}$)

Results from the central laboratory will include the out of range flag based on the lower and upper limits of normal range. Categories will be

- Low CS
 - Low NCS
 - Normal
 - High NCS
 - High CS, and
 - Missing.
-
- 5: 24-h Urinary Free Cortisol and Creatinine

24-hour urine sample will be collected at Visit 2 and at Visit 4 for the measurement of urinary free cortisol and creatinine excretion.

8 Analysis Methods

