- **No administration of study drug will take place at Visit 4.**

Before discharge at Visit 4

- **All study material (study drug, rescue medications, e-diary) will be collected.**
- The investigator will prescribe each subject an appropriate treatment or restore their initial therapy or refer them to their primary care physician.
- An appointment will be made in 1 week time for the follow-up phone call.

7.1.6 (Visit 5) Follow-up Phone Call (Week 9)

A safety follow up phone call will be performed by the investigator or designated staff no later than 1 week after the final visit (V4) or Early Termination Visit to check the status of unresolved AEs and to record any new AEs that may have occurred after V4, as well as related concomitant medications.

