12.3.6 Safety variables

Adverse Events

All adverse events starting on or after the time of first study drug intake will be classified as Treatment Emergent Adverse Events (TEAEs). Any adverse event started after the informed consent signature and before the time of first study drug intake will be classified as pre-treatment adverse event. Pre-treatment adverse events will be listed only.

The number of TEAEs and the number and percentage of subjects who experienced at least one TEAE will be presented by treatment for all AEs, ADRs, serious AEs, serious ADRs, severe AEs, AEs leading to study discontinuation and AEs leading to death. Summaries will be presented overall and by system organ class and preferred term based on the MedDRA dictionary.

Vital signs

Vital signs (systolic and diastolic blood pressure) and their changes from baseline (Visit 2) will be summarized by treatment using descriptive statistics and the 95% CI of the mean.

ECG

12-lead ECG parameters (HR, QTcF, QRS and PR) and their changes from baseline (Visit 2) will be summarized by treatment using descriptive statistics and the CI of the mean (95% CI for absolute values and 90% CI for the changes from baseline).

The number and the percentage of subjects with a:

- QTcF >450ms (males only), >470ms (females only), >480ms (males only) and >500ms
- change from baseline (Visit 2) in QTcF >30ms and >60ms
- at post-baseline visit will be presented by treatment group.

Laboratory parameters

Shift tables from screening to the end of treatment, based on normal ranges, will be presented by treatment group for the laboratory parameters.

Mean change from baseline (Visit 2) to the end of treatment in 24-h urinary free cortisol and creatinine will be calculated with its 95% CI by treatment group.

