3.7 Interim Analyses

No interim analyses are planned for this clinical investigation.

3.8 Changes in the Conduct of Study or Planned Analysis compared to the Study Protocol

No changes in conduct between the Statistical Analysis Plan (SAP) and the study protocol have been noted.

4 General Definitions

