10.7.1 Adverse Events

As defined in the protocol, all AEs starting on or after the date of first study drug intake will be classified as a TEAE. Only TEAEs will be included in the tables. AE onset date will be taken into account when assigning AEs as *treatment emergent*. Pre-treatment AEs (AE onset date < date of first randomized study drug intake) and post-study AEs (AE onset date > date of completion/discontinuation) will be included in the subject listings, and flagged, but will be excluded from other summaries.

The number of TEAEs, serious TEAEs, ADRs, serious ADRs, severe TEAEs, TEAEs leading to study drug discontinuation and TEAEs leading to death, and the number and the percentage of subjects experiencing TEAEs, ADRs, serious TEAEs, serious ADRs, severe TEAEs, TEAEs leading to study drug discontinuation and TEAEs leading to death will be summarized by treatment and overall.

The number and percentage of subjects with at least one AE and the number of AEs will be presented by SOC and PT by treatment and overall for treatment-emergent AEs, ADRs, serious TEAEs, serious ADRs, severe TEAEs, TEAEs leading to study drug discontinuation and TEAEs leading to death.

Subjects who have multiple events in the same system organ class (SOC) and preferred term (PT) will be counted only once in the subject counts.

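### The SAP caps TEAEs at the completion/discontinuation date, against protocol 12.3.6 and SAP 10.7.1, so AEs starting between early discontinuation and the follow-up call are left out of the AE tables

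*SAP*

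**What the plan says.** **Protocol.** Section 12.3.6 states: "All adverse events starting on or after the time of first study drug intake will be classified as Treatment Emergent Adverse Events (TEAEs". It gives no end date, and the only other class is pre-treatment. The synopsis has the same rule. Section 7.1.6 schedules a safety call no later than 1 week after Visit 4 or the Early Termination (ET) visit, in part "to record any new AEs that may have occurred after V4". Table 1 lists AE assessment at that contact (Visit 5), and section 10.8 records AEs until the subject's participation ends.

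**SAP 7.2.11.** TEAEs are "all adverse events starting on or after the first study drug intake, up to study completion/discontinuation". A third class is added: "post-study AE: if AE starts after the date of completion/discontinuation".

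**SAP 10.7.1.** The section opens: "As defined in the protocol, all AEs starting on or after the date of first study drug intake will be classified as a TEAE". It goes on: "Only TEAEs will be included in the tables". Pre-treatment and post-study AEs "will be included in the subject listings, and flagged, but will be excluded from other summaries". Section 11 gives post-study AEs a listing (16.2.7.9) and no table.

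**SAP 3.8.** "No changes in conduct between the Statistical Analysis Plan (SAP) and the study protocol have been noted".

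**The concern.** One derivation flag has two rules. A programmer working from SAP 7.2.11 stops the TEAE window at the completion/discontinuation date. One working from the protocol, or from the first sentence of SAP 10.7.1, does not stop it there. The choice decides which events are tabulated.

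The disputed window is planned safety follow-up, since recording new events is one stated purpose of the call. The tables for serious AEs, ADRs and severe AEs are restricted to TEAEs, and SAP 7.2.11 defines an AE leading to death as a TEAE with a fatal outcome. A fatal event starting two days after withdrawal would therefore be absent from the death table and appear only in a listing. Protocol 4.4 withdraws subjects permanently after a severe exacerbation, so those affected include clinically unstable people.

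**Working it through.** **1. The rules side by side.** Let F be the date of first study drug intake and E the date of completion/discontinuation.

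| Source | TEAE if | Onset after E |
|---|---|---|
| Protocol 12.3.6 | onset ≥ F | TEAE |
| SAP 10.7.1, first sentence | onset ≥ F | TEAE |
| SAP 7.2.11 | F ≤ onset ≤ E | post-study, listing only |

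**2. Where E falls for early terminators.** Protocol 7.1.7 describes a subject who discontinues, then attends an ET visit if possible, then has the call about 1 week later. SAP 7.1 takes the discontinuation date from the Study Termination page as the event date for time to discontinuation. SAP 10.8 uses it when re-allocating diary data. Both uses fit the date the subject left, so E comes before the call.

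**3. Test case.** First dose Day 1, discontinuation and ET visit Day 21, call Day 28.

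| Onset | Protocol | SAP 7.2.11, E = Day 21 | SAP 7.2.11 if E were the call, Day 28 |
|---|---|---|---|
| Days 1, 20, 21 | TEAE | TEAE | TEAE |
| Days 22, 28 | TEAE | post-study | TEAE |

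The rule works on onset date. An AE first reported on Day 28 that began on Day 20 remains a TEAE. Where an incomplete date leaves the class open, SAP 7.2.11 assigns treatment emergent first.

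**4. Completers.** SAP 7.1 censors completers at a date of completion that is not tied to Visit 4 or Visit 5. If it is Visit 5, nothing is lost. If it is Visit 4, the window is up to 7 of 56 + 7 = 63 days, or 11%.

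**5. Size for early terminators.** The plan's number randomized reproduces: 99 / (1 − 0.15) = 116.5, rounded up to 117, and 5 × 117 = 585. Planned treatment time is 585 × 8 = 4,680 subject-weeks. No early-termination rate is given, so I assume 5% to 15%; the upper end borrows the 15% non-evaluable rate. I also assume the ET visit falls on or close to the discontinuation date, so each subject contributes at most about one week.

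- 5%: 585 × 0.05 = 29 subjects (about 6 per arm); 29.25 / 4,680 = 0.6%.
- 15%: 585 × 0.15 = 88 subjects (about 18 per arm); 87.75 / 4,680 = 1.9%.

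**The case against.** The strongest reply is that the discontinuation date is never defined. The SAP has a separate term, the end of the randomized treatment period, for the Visit 4 or ET date, and 7.2.11 does not use it. The protocol numbers the call as Visit 5 and stops AE recording when participation ends. If E means the end of participation, the cap matches the recording limit and nothing scheduled is lost. For completers this stands as an open possibility. For early terminators it is strained, given the order of events in protocol 7.1.7 and the SAP's own uses of the date.

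Second, the window is off treatment. No study drug is given at the ET visit, and the investigator arranges other therapy. Ending the TEAE window is a legitimate choice in principle. What cannot stand is doing so while attributing the open-ended rule to the protocol.

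Third, the SAP is based on protocol version 3.0, the supplied protocol refers to version 4.0, and the SAP 3.8 sentence speaks of conduct. This weakens the charge of an undeclared change, although the heading of 3.8 also covers planned analysis. It does not remove the conflict, because SAP 10.7.1 itself attributes the unbounded rule to its protocol.

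Some stronger readings are tempting but unsupported:

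- **Everything reported at the call is lost.** It is not, because onset date decides. An AE or exacerbation that caused the withdrawal began on or before it and stays in the tables.
- **Every safety table is affected.** Only AE summaries are. Vital signs, ECG, laboratory and urinary cortisol tables are untouched, and the events remain in a flagged listing.
- **15%, or 88 subjects, will withdraw.** That rate is for non-evaluable subjects. Subjects lost to follow-up may have no call at all.
- **The undercount differs between arms.** It could, but the documents give no withdrawal or event rates by arm.

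**Conclusion.** Wrong as written. SAP 7.2.11 conflicts with protocol 12.3.6 and with the first sentence of SAP 10.7.1. If 7.2.11 is followed, AEs starting after early discontinuation and up to the call are collected but kept out of the AE summary tables, including those for serious, drug-related and fatal events.

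The volume is small: at most 29 to 88 subject-weeks under the assumed 5% to 15% early-termination rate. All of it falls on subjects who stopped early. For completers the effect is undetermined until the completion date is defined, and no direction of bias between arms can be stated. The conclusion for early terminators rests on reading the discontinuation date as the day the subject left; it would fail only if sites entered the call date. Sample size and efficacy analyses are unaffected.

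**What to change.** 1. In SAP 7.2.11 and 10.7.1, remove the cap at completion/discontinuation. Count as a TEAE any AE with onset on or after first study drug intake that is recorded during study participation, through the safety follow-up call, or through the last contact if there is no call.
2. State which date completion/discontinuation means, separately for completers and early terminators.
3. Keep the post-study class only for onsets after the last follow-up contact. Protocol 12.3.6 has no such limit, and protocol 10.9 still has SAEs reported after participation ends if the investigator learns of them. Declare this residual limit in SAP 3.8 as a departure.

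The cost is SAP wording and one derivation flag, settled before unblinding. The downside is that AE counts may rise slightly and will include some off-treatment events.

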8.1 General Methods

Hypothesis testing will be carried out at the $\alpha = 0.05$ level (two-sided). Statistical significance will be declared if the p-value is less than 0.05, with p-values for the primary efficacy analysis adjusted for multiplicity as described in Section 8.2.

For **continuous variables**, summary statistics will include the number of non-missing observations, mean, standard deviation, 95% (or otherwise) confidence interval of the mean (only in the efficacy and safety analyses, unless otherwise specified), minimum, median and maximum.

For **qualitative variables**, the number (n) and percentage (%) of subjects with non-missing data per category will be the default summary presentation, and where appropriate and present, the number of missing values as a “Missing” category. Unless otherwise specified, the denominator for each percentage will be the number of non-missing observations within the analysis set and treatment group.

General rules to be used for reporting the number of decimal places for derived variables in the listings (in the analyses rounding will not be performed):

- BMI, treatment exposure (days): whole numbers;
- Time to discontinuation (weeks), duration of smoking (years), time since first asthma diagnosis (years), compliance, average use of rescue medication (number of puffs/day), percentage of rescue medication-free days, asthma symptoms scores, percentage of asthma symptoms-free days, percentage of asthma control days: 1 decimal place;
- Change from baseline/pre-dose: same as the variable considered.

The following rules on decimal places will be considered for the results of the analyses (if the analyses are performed on derived variables, the level of precision of the actual data is derived from the previous list):

- min, max: same as actual data;
- mean and its confidence limits (unadjusted and adjusted), adjusted difference between means and its confidence limits, SD, median: actual data + 1 decimal place;
- percentage: 1 decimal place;
- P-values: 3 decimal places; if the p-value is less than 0.001, it will be presented as <0.001.

In general, additional to the analysis model results presented in TLFs, the full SAS output generated for all the analyses will be presented to the sponsor as a standalone document. SAS output results will be delivered only after DB lock.

Calculation of adjusted means (least squares means):

The approach described below will ensure that the least squares means calculated by SAS will be based on:

- coefficients for classification effects (i.e., the effects of categorical covariates) proportional to the margins observed in the group of subjects analysed;
- effects of quantitative covariates set equal to their mean values in the group of subjects analysed.

The analysis is based on the following steps:

1. generate a dataset by selecting:
 - in case of repeated post-randomisation measurements (e.g., FEV₁ at each visit, analysed using a linear mixed model for repeated measures): all the post-randomisation records for subjects with at least one available and valid post-randomisation measurement and no missing covariates;
2. in case of repeated post-randomisation measurements, add to the dataset generated in step 1 the records for missing post-randomisation visits of the subjects included in the dataset. In the added records the value of the response variable will be missing, but the full information on covariates has to be included;
3. use the dataset obtained as the input dataset for the MIXED procedure, specifying the following options in the LSMEANS statement:
 - in case of repeated post-randomisation measurements: OM AT MEANS;

Example: analysis of change from baseline (Visit 2) at all visits (Visits 3 to 5) based on a mixed model for repeated measures including the effects of treatment, visit (categorical variable), treatment by visit interaction, baseline and another covariate. Visit 1 represents the screening visit.

Original dataset (X = available value, . = missing or invalid value):

| Patient | Treatment | Covariate | Baseline | Visit | Change from baseline |
|---------|-----------|-----------|----------|-------|----------------------|
| 1 | A | X | X | 1 | . |
| 1 | A | X | X | 2 | . |
| 1 | A | X | X | 3 | X |
| 1 | A | X | X | 4 | X |
| 1 | A | X | X | 5 | X |
| 2 | B | X | X | 1 | . |
| 2 | B | X | X | 2 | . |
| 2 | B | X | X | 3 | X |
| 3 | A | X | X | 1 | . |
| 3 | A | X | X | 2 | . |
| 3 | A | X | X | 3 | X |
| 3 | A | X | X | 4 | . |
| 3 | A | X | X | 5 | X |
| 4 | B | X | X | 1 | . |
| 4 | B | X | X | 2 | . |
| 5 | A | . | X | 1 | . |
| 5 | A | . | X | 2 | . |
| 5 | A | . | X | 3 | X |

Step 1 (visits 1 and 2 not selected since pre-randomisation, subject 4 not selected due to missing post-randomisation measurements, subject 5 not selected due to missing covariate):

| Subject | Treatment | Covariate | Baseline | Visit | Change from baseline |
|---------|-----------|-----------|----------|-------|----------------------|
| 1 | A | X | X | 3 | X |
| 1 | A | X | X | 4 | X |
| 1 | A | X | X | 5 | X |
| 2 | B | X | X | 3 | X |
| 3 | A | X | X | 3 | X |
| 3 | A | X | X | 4 | . |
| 3 | A | X | X | 5 | X |

Step 2 (added records in *italic*):

| Subject | Treatment | Covariate | Baseline | Visit | Change from baseline |
|---------|-----------|-----------|----------|-------|----------------------|
| 1 | A | X | X | 3 | X |
| 1 | A | X | X | 4 | X |
| 1 | A | X | X | 5 | X |
| 2 | B | X | X | 3 | X |
| 2 | B | X | X | 4 | . |
| 2 | B | X | X | 5 | . |
| 3 | A | X | X | 3 | X |
| 3 | A | X | X | 4 | . |
| 3 | A | X | X | 5 | X |

